study will primarily evaluate feasibility and acceptability of a real-world sleep intervention frequently employed in the pediatric TBI population within the outpatient setting. We will also explore whether earlier inpatient employment of standard SWD interventions (melatonin and sleep education) commonly administered in the outpatient setting can provide benefit when employed earlier in the disease course as an adjuvant to clinical TBI care.

4. Study Design

This is a pilot randomized controlled phase II intervention trial evaluating early melatonin and sleep education via handouts versus placebo following pediatric traumatic brain injury (TBI) in two parallel study arms. This single center trial will focus on feasibility and acceptability outcomes, but will also obtain data on clinical effectiveness to reduce sleep wake disturbances at 30-day outcomes assessment. Sleep disturbances (with questionnaires and actigraphy data from Fitbits), feasibility (with clinical data collection, participant survey), and acceptability (survey, medical chart review) outcomes will be collected.

The intervention of this study uses a dietary supplement (melatonin) and an educational intervention administered via handouts. This study is not designed to evaluate melatonin's therapeutic efficacy or potential to diagnose, cure, mitigate, or otherwise treat a specific medical disorder, only to evaluate potential benefits to the bodily function of sleep when used with sleep education. The combined intervention of melatonin and sleep education was designed to mirror real world clinical care employed in this population within the outpatient setting in order to be generalizable to a heterogeneous population that is representative of the pediatric TBI population; therefore, our trial is designed to be pragmatic and will be exploring effectiveness outcomes for SWD relevant to this population, rather than efficacy of any one part of the intervention. A primary focus will be feasibility and acceptability (including intervention usage) to inform a larger longitudinal trial that would be needed to account for unavoidable population heterogeneity in clinical characteristics and adherence to intervention recommendations within the clinical setting.

5. Study Population

a. Number of Subjects

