We expect to enroll between 30-50 patients based on eligibility over 2.5 years of recruitment. This estimate is based on the most recent hospital admissions data since the start of the COVID-19 pandemic estimating approximately 100 patients will qualify for the study over 2.5 years. Participants will be randomized 1:1 to receive the intervention. Recruitment and retention will be assessed during the trial as outcomes.

b. Inclusion and Exclusion Criteria

Children \geq 6 years and <19 years of age admitted with TBI (defined as injury to the head from external forces with severity mild, moderate, or severe classified by Glasgow Coma Scale) will be included.

Children under the age of 6 years will be excluded due to increased variability in baseline sleep patterns, daytime napping, and lack of standardized tools identifying sleep outcomes between children younger and older than 6 years. Patients over age 18 years will be excluded as they are primarily treated in adult care units and the study focus is pediatric. Patients unable to tolerate enteral medications within 72 hours of hospital admission, as defined by the clinical care Attending Physician, will be excluded from the study. Patients undergoing dialysis, requiring extracorporeal life support, or with significant liver dysfunction (defined as aspartate aminotransferase (AST) or alanine aminotransferase (ALT) more than 2 times the upper limit of normal for age) will be excluded. Patients about whom the Attending Physician has any safety

concerns regarding use of melatonin as per clinical judgement will be excluded from the study. Patients with abusive trauma will be excluded. Suspected or known prisoners are excluded. Pregnant patients are excluded. There will be no requirement for contraception during the trial in female patients of child-bearing age. Patients must have a parent or guardian with whom they reside in order to participate in the study given the parent-reported measures used for outcomes.

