Text messaging will be used for system generated reminder prompts such as "Please sync your device"; or if battery is low, "Please charge your battery" during the 1-month study period while participants wear the Fitbit. Text messaging functions require sharing of participant phone numbers with the Fitabase platform and Twilio, Inc.

Feasibility benchmarks will be assessed every 6 months during the trial. If feasibility benchmarks are not met, study procedures and the protocol will be reviewed using input from stakeholders and preliminary data to determine if changes are warranted.

Table 1. Outcomes Evaluation and Analysis for Melatonin Trial

Outcome (time collected)	Measurement or Assessment Tool	Analysis
Feasibility Outcomes		
*Recruitment (6-monthly feasibility reviews)	Number subjects consented/approached; goal >50%	Descriptive percent
*Retention (6-monthly feasibility reviews)	Quantitative Number completed/consented; Goal >90%	Descriptive percent
Screen failure (6-monthly feasibility reviews)	Number approached/eligible patients; expect <<5%; eligible patients will be derived from the OHSU Trauma Registry and compared to study logs	Descriptive percent
Reasons for Participation/ Non-participation (time of approach/consent)	Qualitative response to survey: "Please describe reasons you chose [not to or to] participate in this research study"; "Could the study team do something different in the future to increase chances you would participate in future studies?"	Thematic analysis
Reasons for drop-out (30-day)	Qualitative response to survey: "We would like to know how we can improve our study in the future. Please tell us your reasons for leaving the trial"; "How could the study team have assisted you better in completing the trial?"	Thematic analysis
Adherence (30-day)	Pill counts: adherent if \geq 75% prescribed pills are taken at the follow-up study visit; will be counted as unknown if pill count not available Sleep tracking usage: actigraphy data and sleep diaries will be compared to age based recommendations; actigraphy counted as	Descriptive percent; Chi-square to compare intervention arms Descriptive percent; Chi-square to compare intervention arms

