a. Sharing of Results with Subjects

Data from this clinical trial will not be shared directly with participants. The results of the clinical trial and de-identified data will be made in accordance with NIH regulations and clinicaltrials.gov.

b. Data and Specimen Banking

No specimens will be stored. Study records will be retained for the longest regulatory retention period. After that time, records will be destroyed in a confidential manner.

8. Data Analysis

See Table 1 for outline of data analysis planned for study outcomes. As this is a pilot intervention trial, the focus will be on feasibility and acceptability of the pragmatic intervention trial. We will also explore effectiveness outcomes, but recognized we will be underpowered for a definitive effectiveness trial within this heterogeneous population selected to be representative of the population of interest. We will use our pilot trial to inform a future larger trial that will include longitudinal real world health outcomes relevant to the pediatric TBI population if supported by our preliminary results.

Prior to evaluating outcomes, we will perform a thorough descriptive analysis of participant baseline characteristics (age, race, ethnicity, gender, pre-injury comorbidities, TBI characteristics including severity, location, and type). We will examine patterns of missingness in our outcomes collected at 1-month, differences in participant and non-participant characteristics, and differences in participants who completed versus dropped out of the study to ascertain potential bias. Additionally, we will describe and compare the distribution of patient and clinical characteristics, including age and TBI severity, across treatment groups to ensure our randomization protocol was successful. Comparisons between groups will be made using chi-square tests for categorical variables. Depending on characteristics of the data, t-tests and Mann-Whitney U tests will be used to compare continuous variables between groups. We plan to perform both intention to treat and per protocol analyses.

Quantitative feasibility outcomes will be presented as a percentage of patients, the denominators of which are listed in Table 1. Comparisons between groups will be made with chi-square tests.

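### Pill-count adherence is reported only as the share of children at or above 75% of pills, so the pilot would not report how many doses were taken or how that varied, and the between-arm test can lose power when adherence shifts gradually

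*Combined protocol and SAP*

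**What the plan says.** In section 6, the Adherence (30-day) row of Table 1 defines the pill-count measure as "Pill counts: adherent if \geq 75% prescribed pills are taken at the follow-up study visit". A missing count "will be counted as unknown if pill count not available". The analysis column reads "Descriptive percent; Chi-square to compare intervention arms".

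Section 8 repeats this: "Quantitative feasibility outcomes will be presented as a percentage of patients, the denominators of which are listed in Table 1", followed by "Comparisons between groups will be made with chi-square tests". No average, median, spread or full-scale comparison of pills taken appears in either place, and no reason is given for the 75% threshold.

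Section 4 states why usage matters: "A primary focus will be feasibility and acceptability (including intervention usage) to inform a larger longitudinal trial". Adherence carries no primary-outcome asterisk in Table 1.

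The plan treats adverse events more fully. They are kept both as yes/no (chi-square) and as a number per patient (Mann-Whitney U). The count is summarised by mean and SD in Table 1 and by median and IQR in section 8.

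**The concern.** Section 6 has the study product taken nightly for 30 days, so a pill count can take about 31 values. The plan reduces these to two. Pill count is also the only measure of study-drug use in Table 1 that does not rely on recall. The other is a five-category self-report of nights per week, and the Fitbit item concerns device wear and sleep.

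Two things are at stake. The main one is description: designers of the larger trial would learn what share of children passed a threshold, but not the average share of doses taken or its variation, which they need in order to allow for dilution of the effect. The lesser one is sensitivity: if one arm takes somewhat fewer doses across the board, most children may stay on the same side of 75% and the chi-square may miss it.

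**Working it through.** The plan states no power, alpha, expected adherence or effect size for this outcome, so it has no figure to reproduce.

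**Inputs from the documents.** Cut at 75%; about 30 nightly doses; "We expect to enroll between 30-50 patients based on eligibility over 2.5 years of recruitment"; "Participants will be randomized 1:1 to receive the intervention". This gives 30/2 = 15 to 50/2 = 25 per arm if every child has a pill count; unknown counts would lower it.

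**Assumed.** Two-sided 5% test; pills taken ~ Binomial(30, p), with p ~ Beta(mean × k, (1 − mean) × k), where k is the precision; the mean adherence values shown below.

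**Step 1: what the cut hides.** 0.75 × 30 = 22.5, so adherent means 23 or more pills. Then 23/30 = 76.7% is grouped with 30/30 = 100%, and 22/30 = 73.3% with 0/30. If a share π of children meets the cut, the mean share of doses taken can lie between

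- lower limit: π × 23/30 + (1 − π) × 0
- upper limit: π × 1 + (1 − π) × 22/30

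At π = 0.80, chosen only for illustration, the limits are 0.80 × 0.767 = 61.3% and 0.80 + 0.20 × 0.733 = 94.7%. The planned percentage leaves a range of 33 points. This step needs no distributional assumption.

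**Step 2: power under gradual shifts.** Simulated power (%) of Mann-Whitney U on percent taken, uncorrected chi-square on the 75% cut, and the difference in points:

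| Mean adherence | k | Per arm | Mann-Whitney | Chi-square | Loss |
|---|---|---|---|---|---|
| 95% v 85% | 4 | 15 | 63.4 | 21.9 | 41.5 |
| 95% v 85% | 4 | 25 | 85.0 | 41.9 | 43.1 |
| 90% v 80% | 4 | 15 | 42.5 | 23.3 | 19.2 |
| 90% v 80% | 4 | 25 | 64.1 | 36.6 | 27.5 |
| 85% v 70% | 4 | 15 | 56.8 | 39.8 | 17.0 |
| 85% v 70% | 4 | 25 | 79.7 | 61.6 | 18.1 |
| 85% v 70% | 6 | 15 | 64.1 | 47.4 | 16.7 |
| 85% v 70% | 6 | 25 | 89.0 | 73.4 | 15.6 |
| 95% v 85% | 10 | 15 | 83.1 | 22.1 | 61.0 |
| 90% v 70% | 10 | 25 | 100.0 | 97.7 | 2.3 |

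The k = 4 rows used 4,000 simulated trials each. The others come from a separate grid of 54 scenarios (k = 3, 6, 10; nine pairs of means; 15 and 25 per arm) with 1,000 trials each. The last two rows are that grid's extremes; the full scale had higher power in all 54. With no true difference (both means 85%), rejection rates were 4.8 to 5.6% for chi-square and 4.6 to 5.0% for Mann-Whitney. The plan does not say whether a continuity correction applies; with one, the losses in the grid were 5 to 80 points.

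**Step 3: where the loss shrinks or reverses.** In a normal approximation with a 0.3 SD shift, the loss was only 3 to 11 points, with power low either way (13 to 18% against 6 to 13%). If the arms differ only in the share who stop outright (10% v 40%, others near 90% of doses), the cut does better: 44.8% against 28.8% at 15 per arm and 68.1% against 45.5% at 25. Over stopping rates of 10–20% v 40–50%, its advantage was 12 to 26 points.

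**Step 4: small cells.** If 90% and 75% of the arms met the cut, the pooled non-adherent share is (10% + 25%)/2 = 17.5%. The expected non-adherent count per arm is 15 × 0.175 = 2.6 or 25 × 0.175 = 4.4, both below 5. No exact test is named.

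**The case against.** The strongest reply is that power is the wrong yardstick. Adherence is not marked primary, the pilot sets no hypothesis for it, participants are blinded, and section 6 gives both arms a study product and the same handout. Nothing in the documents predicts the 10 to 20 point gaps assumed above. This stands, and it is why the descriptive loss in step 1 carries the point.

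Second, sections 6 and 7 let participants discontinue the intervention, which is the pattern where the cut performs better. This also stands, and it argues for keeping the threshold test.

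Third, the 95% v 85% case is heavy at the ceiling. At k = 4 and 15 per arm, about 63% v 24% of children take all 30 pills. A yes/no split at 30/30 has 57% power, against 64% for Mann-Whitney and 22% for the 75% cut. Much of the gain there reflects where the cut falls, and a random miscount of up to 2 pills lowers Mann-Whitney to 46%. This limits how much weight that row can bear.

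A reader might also infer that a fall in doses would go unseen. The documents do not support that: Table 1 asks about nights taken and reasons for not taking the medication, and compares a symptom list by arm. These complement a summary of doses taken but do not replace it. Nor is a fixed threshold, or its missing rationale, an error in itself; benchmarks are usual in feasibility work.

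**Conclusion.** The point holds as a loss of information. As written, the pilot would not report the average or spread of doses taken, although usage is meant to inform the larger trial. That conclusion rests only on the plan's text and the 30-night course.

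The power argument is secondary and conditional. For gradual shifts the loss was roughly 2 to 60 points under assumed beta-binomial pill-taking with 15 or 25 per arm; it is small for very small shifts and reverses under all-or-none stopping. A reader might take some such range as the fixed cost of the cut, or conclude that the chi-square is invalid. Neither follows: the documents give no adherence distribution, so no range is a bound, and the uncorrected test's error rate was about 5% in the no-difference scenario simulated. The matter is modest for a non-primary pilot outcome, but worth correcting because it costs almost nothing.

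**What to change.** In the Table 1 Adherence row and in section 8:

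- Keep the percentage of children at or above 75% and its chi-square between arms.
- Add the percentage of prescribed pills taken (0–100%), summarised as median and IQR, plus mean and SD for planning the larger trial, overall and by arm.
- Add a Mann-Whitney U comparison of that percentage, labelled exploratory, in line with the handling of adverse-event counts.

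The cost is a few lines of wording, one more summary and one more exploratory test on a non-primary outcome. The pill counts are already collected, so no new data or procedures are needed. Specifying this now avoids a post hoc choice of summary.

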Participants and study staff assessing outcomes will be blinded to intervention status. Research assistants on the study staff will add the sleep education handouts with video links to discharge instructions to be delivered by the bedside nurse in concurrence with clinical care. The intervention was designed this way to increase feasibility and generalizability for the future by providing a means of information dissemination that could be easily and widely adopted if effective within different health systems in conjunction with clinical care. This research assistant will be notified by REDCap when a participant is enrolled, and will place instructions in the discharge section of the electronic health record that is automatically printed at discharge, without interaction with other study team members or families. Additionally, this portion of the intervention will be delivered at hospital discharge concurrent with clinical care to improve generalizability in future work by limiting change to institutional care practices. The sleep handout will be delivered in conjunction with standard discharge instructions provided to all TBI patients and other care will remain per our institutional TBI standards directed by the

patient's care team (an example of these standard TBI discharge instructions are uploaded in supporting documentation).

Outcomes: We will include measures of feasibility, acceptability, and effectiveness. See **Table 1** for summary of outcomes and schedule of collection. Outcomes will be assessed at hospital discharge, and a study visit at 30 days \pm 17 days. 30-day outcomes assessments will be defined from the time of study intervention initiation. The primary outcomes will be measures of feasibility and acceptability, with exploration of effectiveness in this pilot trial. Quantitative measures of recruitment and retention (feasibility), adverse events and utilization (acceptability), and total score of the Sleep Disturbances Scale for Children (SDSC) at 30-days (clinical effectiveness) will be used. Outcomes will be collected by the study team over the phone, via chart review, or via electronic survey administered through REDCap. Secondary and other outcome measures will be collected by activity monitor, chart review, survey, sleep questionnaire, and actigraphy devices. Fitbits will be worn continuously during the 30 day study period except when removed for charging the device.

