	
adherent if device worn for ≥5 nights consecutively; we will assess sleep routines through actigraphy; will be counted as unknown if did not participate in the actigraphy portion
 
Quantitative survey: "How many nights each week did you take the study medication since discharge?"
 
None, 1-3, 3-4, 5-7, All
 
Quantitative survey response: "Did you receive sleep education with your hospital discharge paperwork?"; choices of a) did not receive discharge paperwork; b) I did not receive any sleep education at discharge; c) I received it, but did not use it; d) I received it, but did not find it helpful; e) I received it, and found it helpful; responses to this question will also be compared with the discharge instructions within the electronic health record to determine if the resource was provided as intended.
	Descriptive percent; Chi-square to compare intervention arms
Acceptability Outcomes		
*Adverse Events (discharge, 30-day)	
Qualitative response to survey: "Did you have any new medical problems since the last study visit?"
 
Quantitative yes/no response: "Did you have any of the following symptoms since the last visit"
 
 a. Nausea b. Vomiting c. Diarrhea d. Drowsiness e. Fatigue f. Headache g. Behavioral changes h. Vivid dreams i. Nightmares j. Waking up at night k. Itchy skin l. Rash m. Appetite changes n. Bodily pain or aches o. Chest pain p. Enuresis or bedwetting q. Dizziness r. Tinnitus or ringing in the ears s. Feeling cold 
Evaluation of medical record, patient assessments to quantify adverse events and unexpected problems collected as a dichotomized yes/no and number of events
	
Thematic analysis
 
Descriptive percent and mean with standard deviation; Chi-square (yes/no) and Mann-Whitney U test (continuous) to compare intervention arms

Satisfaction (30-day)	Quantitative rankings on a likert scale survey: experiences with the study overall, consent process, study team, study intervention, questionnaires, Actigraphy devices, care received	Descriptive median and interquartile range; Mann-Whitney U tests

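### The nights-per-week answer options for study medication in Table 1 overlap at 3 nights and, as printed, at 7 nights

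*Combined protocol and SAP*

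**What the plan says.** The Adherence (30-day) row of Table 1, in Section 6 (Procedures Involved), lists several measures. One is a survey question to the family: "How many nights each week did you take the study medication since discharge". Its printed answers are "None, 1-3, 3-4, 5-7, All". The analysis given for adherence items in that row is "Descriptive percent; Chi-square to compare intervention arms".

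The same row defines pill-count adherence as at least 75% of prescribed pills, with an unknown category when no count is available. It counts actigraphy as "adherent if device worn for ≥5 nights consecutively", and a participant "will be counted as unknown if did not participate in the actigraphy portion".

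Three other places bear on the point:

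- Section 4 (Study Design): "A primary focus will be feasibility and acceptability (including intervention usage) to inform a larger longitudinal trial".
- Section 5a (Number of Subjects): "We expect to enroll between 30-50 patients", randomized 1:1.
- Section 6, Outcomes: "Fitbits will be worn continuously during the 30 day study period except when removed for charging the device".

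**The concern.** A categorical survey item can be tabulated without ambiguity only if every answer belongs to exactly one box. Here a family that gave the medication three nights a week may tick either of two boxes and be right both times. The same is true at seven nights on the plain reading of the options. Families with identical use can then land in different categories, and the percentages by arm and the chi-square pick up that difference.

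The stake is modest but real. Usage of the intervention is one of the things the pilot is meant to tell the designers of a larger trial. Where the pill count is unknown, this question is the remaining direct measure of medication intake in the table.

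**Working it through.** The plan gives no figure of its own on this point, so there is nothing to reproduce. The check has three steps.

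**1. Which boxes contain each possible answer.** The inputs are the printed options and whole nights from 0 to 7, with All read as 7 nights a week.

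| Nights per week | Share of 7 nights | Boxes that fit |
|---|---|---|
| 0 | 0% | None |
| 1 | 14% | 1-3 |
| 2 | 29% | 1-3 |
| 3 | 43% | 1-3 and 3-4 |
| 4 | 57% | 3-4 |
| 5 | 71% | 5-7 |
| 6 | 86% | 5-7 |
| 7 | 100% | 5-7 and All |

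There are two overlaps and no gaps. If All instead means every night since discharge, a family that usually gave seven nights but missed one early on would belong in 5-7. The table does not say which meaning applies.

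**2. Weight of one family.** The inputs are 30 to 50 patients in two equal arms, so 30/2 = 15 to 50/2 = 25 per arm before drop-out. One family is 1/25 = 4.0 to 1/15 = 6.7 percentage points of its arm.

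As an illustration, take 15 per arm and one family at three nights in each arm, one ticking 1-3 and the other 3-4. The arms then differ by 6.7 points in each of those two categories, although use is identical. If fewer families answer, each weighs more. The documents give no basis for how many families will be at three or at seven nights.

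**3. The device rule, for context.** Five nights out of 30 planned is 5/30 = 17%. The share is larger when the device was available for fewer nights. Section 11a allows devices to be mailed, and Section 6 sets the follow-up visit at 30 ± 17 days. If, as an assumption, wear were counted only up to a visit at 30 − 17 = 13 days, five nights would be 5/13 = 38%. The rule is not lenient for every pattern either: a child who misses every fifth night wears the device on 24 of 30 nights (80%) and never reaches a run of five.

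**The case against.** **The consequence at three nights is very small.** Both candidate boxes lie below the only medication-adherence threshold in the plan, 75% of pills, which corresponds to 0.75 × 7 = 5.25 nights a week. Either tick describes low use. This stands, and it is one reason the point is minor. It does not apply at seven nights, where the choice is between full use and a box that also holds 5 and 6 nights.

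**The survey form itself is not in the documents.** The overlap may be a slip in Table 1 only. This also stands. The finding is certain for the printed text and says nothing about answers already collected, so the fix begins with the form.

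**Stronger readings that a reader might infer.** The documents do not support these:

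- *The overlap biases the comparison between arms.* Section 6 says participants are blinded, and nothing suggests that the arms would choose between valid boxes differently.
- *Three nights is the main problem.* Nightly use is the prescribed regimen, so the overlap at seven may touch more families. Which one matters more is unknown.
- *The 5-night device rule is an error.* It is stated openly, no passage contradicts it, and no benchmark depends on it. The Fitbit is a measuring device, and under Section 7 participants may withdraw from that portion. Five nights may simply be a minimum for usable data.
- *Adherence is a starred primary outcome.* The Outcomes text in Section 6 mentions utilization among the acceptability measures, but the adherence row in Table 1 has no star and no target.

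**Conclusion.** As printed, the answer options are not mutually exclusive, and nothing in the document says how to code an answer that fits two boxes. The overlap at three nights needs no assumption. The overlap at seven rests on reading All as seven nights a week.

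Each affected family shifts about 4 to 7 percentage points of its arm between categories, assuming 15 to 25 patients per arm and no drop-out. The expected effect is noise in a descriptive table and its chi-square, not a systematic difference between arms.

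Severity is minor: the measure is unstarred, it has no numerical goal, and the pill count measures intake separately. The device rule is not part of the fault. It prompts only an optional addition to the reporting.

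**What to change.** **Check the form in use.** If its options are already exclusive, correct Table 1 and stop there.

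**If the form has the overlap**, change it for the remaining respondents. Either use exclusive options, for example 0, 1-2, 3-4, 5-6 and 7 nights, or ask for the exact number from 0 to 7. The exact number keeps more detail: a 5-6 box still spans the 75% level, since 5/7 = 71% and 6/7 = 86%.

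**For answers already collected on the overlapping form**, pool 1-3 with 3-4. Where old and new forms are combined, also pool 5-7 with All, because an old seven-night answer may sit in either box. The combined table then has three groups that mean the same on both forms: 0, 1-4 and 5-7 nights.

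**Optional, with the 5-night rule unchanged:** report by arm the nights the Fitbit was worn out of the nights it was available, from data already collected, and keep the planned unknown category.

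**Cost:** a small edit to one survey item and to the table, with no change to treatment, eligibility or sample size. The downside is lost detail. The three-group table cannot separate full use from five or six nights a week, so the pill count would have to carry that distinction where it is available.
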